6.1 Schedule of Evaluations

Assessment	Eligibility Screening (phone/online interview)	Enrollment /Randomization	Baseline (phone/online interview)	8-weeks post baseline (phone/on line interview)	24-weeks post baseline (phone/on line interview)
Eligibility Screening Verbal Consent	X				
Inclusion/Exclusion Criteria	X				
Study Informed Consent Signed		X			
Caregiver/Care Recipient Socio-demographics			X		
Caregiver/Care Recipient Situational Characteristics			X		
Caregiver Chronic Grief			X	X	X
Caregiver Depressive Symptoms			X	X	X
Caregiver Anxiety Symptoms			X	X	X
Caregiver Positive States of Mind			X	X	X
Conflict with Facility Staff			X	X	X
Satisfaction with Care			X	X	X
Caregiver Knowledge of ADRD			X	X	X
Caregiver Sense of Loss			X	X	X
Caregiver Guilt			X	X	X
Caregiver Role Captivity			X	X	X
Caregiver Adherence to CGMI-V Survey (Satisfaction Survey)				X	X
Change in status survey (CG/CR)				X	X

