6.2 Description of Evaluations

Study evaluations consist of: (1) eligibility screening for inclusion criteria, (2) Baseline assessment immediately after enrollment, (3) 8-weeks post-baseline, for intervention effects, and (4) 24-weeks post-baseline for maintenance effects.

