6.2.1 Screening Evaluation

Consenting Procedure

The Project Director will schedule a phone or online screening interview with caregivers expressing an interest in the study. The Project Director will explain the screening process and the questionnaires used to ascertain participant eligibility and invite any caregiver questions. After all questions are addressed, verbal consent to screening will be documented after the screener explicitly asks the caregivers if they consent.

Screening

Caregivers who verbally consent will be screened using computer-assisted telephone interviewing (CATI) for the following inclusion criteria:

- 21 years of age or older
- Identified as family member, fictive kin (self-identified family member) or partner of care recipient
- Within the first two years of care recipient's permanent placement in a long-term care facility (LTCF)
- Care recipient is a resident in a dementia or memory care unit in the LTCF, where a diagnosis of ADRD is mandatory
- Possessing self-reported basic computer literacy and in-home internet access
- Able to speak, read, and write English
- Not currently attending another ADRD caregiver grief management group
- Experiencing high to moderate levels of grief per screening with the Marwit-Meuser Caregiver Grief Inventory-Short Form³⁸ (scores 25 or above), and/or experiencing high levels of depressive symptoms per screening with PHQ9³⁹ (scores 10 or above)

Caregivers meeting all eligibility criteria will be sent a consent form including detailed information about the study. A phone or online meeting will be scheduled with the PI or the Project Director within the next 24-48 hours for discussion of study,

content of consent form, and to respond to any other questions.

Enrollment

Participants will be enrolled into the study once their signed study informed consents are being returned to study office. A baseline appointment will be scheduled within the next 24-48 hours.

Baseline Assessments

Participants who are enrolled into the study, will be assessed at baseline using CATI, for the following outcomes:

- Caregiver and care recipient socio demographics
- Caregiver and care recipient situational characteristics
- Caregiver grief
- Caregiver depressive symptoms
- Caregiver anxiety symptoms
- Caregiver positive states of mind
- Caregiver conflict with facility staff
- Caregiver satisfaction with care in the facility
- Caregiver knowledge of ADRD
- Caregiver sense of loss
- Caregiver guilt

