- Caregiver role captivity

Randomization

The study will be implemented in six waves. Beginning in Month 5 of the study, we will start recruiting and enrolling 24 caregivers for Wave 1, who will be randomly assigned to either the CGMI-V condition ($n = 12$; 6/group) or MT control condition ($n = 12$). After these 24 caregivers have been enrolled, the study team will start recruiting and enrolling an additional 24 caregivers for Wave 2. There will be a total of six waves. Each wave will have 8 weeks to recruit, screen, enroll, randomize to condition, and complete baseline data collection, followed by CGMI-V implementation over 8 consecutive weeks (Figure 1).

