7.2 Methods and Timing for Assessing, Recording, and Analyzing Safety Parameters

CGMI-V is a low risk behavioral intervention designed to support ADRD caregivers emotionally within the first two years of placement of a family member with ADRD in a long-term care facility. The proposed intervention poses minimal risk to participants.

Identified safety parameters identified above in 7.1 will be assessed at: pre-enrollment screening, and the three data collection points (baseline and 8 and 24-weeks).

Interventionists will implement suicide protocol in the event of reported suicidal ideation during group sessions.

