9.2.1 Treatment Assignment Procedures

The study is a Stage I longitudinal randomized clinical trial. ADRD caregivers whose family members are in LCTFs will be recruited, screened for inclusion criteria, and randomly assigned to either CGMI-V or a Minimal Treatment (MT) control condition. Randomization will be stratified in six Waves of 24 participants each, to insure that there are exactly 12 participants in each condition. In Wave 1, we will randomly assign the first 24 enrolled participants to either the CGMI-V condition ($n = 12$; 6/group) or MT control condition ($n = 12$). The same process will continue for the next five Waves. Recruiters and data collectors will be blinded as to the random assignment of each participant. Once caregivers sign the consent to enroll in the study, the Project Director will use randomization software to assign each enrolled participant to CGMI-V or the MT condition. The Project Director will then inform the participants directly of their assignments and ask them to maintain confidentiality about their assignment at data collection points.

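### Section 9.2.1 allows caregivers to be randomised and told their arm before the self-reported baseline; other sections conflict on the order, and no sentence requires baseline first

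*Combined protocol and SAP*

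**What the plan says.** Section 9.2.1 (Treatment Assignment Procedures) gives the allocation rule: "Once caregivers sign the consent to enroll in the study, the Project Director will use randomization software to assign each enrolled participant" to CGMI-V or MT. It continues: "The Project Director will then inform the participants directly of their assignments". The Project Director is also to "ask them to maintain confidentiality about their assignment at data collection points", and section 7.2 counts baseline among "the three data collection points (baseline and 8 and 24-weeks".

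Section 6.2.1 treats a caregiver as enrolled when the signed consent reaches the study office, and then says: "A baseline appointment will be scheduled within the next 24-48 hours". Section 6.2 describes a "Baseline assessment immediately after enrollment". In the schedule (6.1), the column headed "Enrollment /Randomization" stands before the Baseline column. The Randomization paragraph of 6.2.1 says: "Each wave will have 8 weeks to recruit, screen, enroll, randomize to condition, and complete baseline data collection". The implementation paragraph of section 3 gives the same sequence.

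Other text points the other way or is silent. Within 6.2.1 the Baseline Assessments heading comes before the Randomization heading. The wave description in 4.3 mentions recruitment, screening and baseline without placing randomisation before baseline. Section 9.2.1 also speaks of assigning the first 24 enrolled in Wave 1, which can mean that allocation waits for a full wave.

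**The concern.** Every outcome and mediator is the caregiver's own report or test answers: MM-CGI, CES-D, STAI, PSOMS, the FPCR subscales, FPCT and FKAT. Only recruiters and data collectors are blinded. A blinded interviewer limits interviewer bias but cannot stop a caregiver's answers from reflecting the news of being given a live group programme or mailed written material.

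Section 9.5 states Aim 1 as an effect on changes in grief, judged by interaction effects in a multilevel model over three time points. Baseline is one of those points, and baseline grief is not among the listed covariates. If allocation moves the baseline, the reference for every change objective is no longer a pre-allocation measure. The Aim 4 residualised change scores are also built on baseline. Section 9.5 uses the interaction effects to judge whether a larger trial is justified, so a biased estimate bears directly on that decision. A larger sample would not reduce the bias.

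**Working it through.** **Order of events, side by side**

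- 9.2.1: consent, assignment, disclosure. No completed baseline is required.
- 9.2.1 with 7.2: caregivers who have been told their arm are asked for discretion at data collection points, and baseline is one of these.
- 6.1: the Enrollment/Randomization column precedes Baseline, although its only marked entry is signed consent.
- Sections 3 and 6.2.1 (wave text): enrol, randomise, complete baseline.
- 6.2.1 (heading order): baseline, then randomisation.
- 4.3 (wave text): randomisation is not placed relative to baseline.
- 9.2.1 (first 24 enrolled): compatible with waiting for a full wave. Since enrolment means returned consent, a full wave does not guarantee that its last members have been interviewed.

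Most of the text puts assignment first, some suggests the opposite, and nothing makes baseline a condition of assignment or disclosure.

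**Inputs**

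- SD of MM-CGI total 35.78, 64 per arm, 10% attrition: section 9.2.
- Test-retest values .71 to .75 for the MM-CGI: section 9.1, used here as a stand-in for the baseline-to-follow-up correlation r.
- Shift in baseline caused by knowing the arm: not in the documents. I assume 0.1 to 0.2 SD for illustration.

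**The plan's own figure**

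- SE = 35.78/√64 = 4.47; half-width = 1.96 × 4.4725 = 8.77, or 0.245 SD. This reproduces section 9.2.
- 64/(1 − 0.10) = 71.1, rounded up to 72 per arm. This also reproduces.
- The 4.47 is the SE of one arm's mean. For a plain difference between two arms, SE = 35.78 × √(2/64) = 6.33 and the half-width is 12.40 (0.35 SD).
- For a difference in change, SE = 35.78 × √(2(1 − r)) × √(2/64), which equals 4.47 only at r = .75. The plan does not state that assumption.

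**Effect of a baseline shift on change**

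Let allocation move the baseline difference between arms by b. A change contrast is the follow-up difference minus the baseline difference, so its bias has size b. I take the condition-by-time effect as change from baseline to a given follow-up; section 9.5 does not state how time is coded.

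- 0.1 SD: b = 0.1 × 35.78 = 3.58 units; 3.58/8.77 = 41%; 3.58/12.40 = 29%.
- 0.2 SD: b = 0.2 × 35.78 = 7.16 units; 7.16/8.77 = 82%; 7.16/12.40 = 58%.

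**Effect on baseline-residualised scores**

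With equal SDs at the two times, the slope of follow-up on baseline is about r, so the predicted score moves by r × b and the residual is biased by the same amount.

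- 0.1 SD: 3.58 × .71 = 2.54 to 3.58 × .75 = 2.68 units.
- 0.2 SD: 7.16 × .71 = 5.08 to 7.16 × .75 = 5.37 units.

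Adjusting for baseline therefore reduces the bias but does not remove it.

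**Direction**

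Disappointed MT caregivers would start with higher grief scores, and hopeful CGMI-V caregivers with lower ones. Either pattern makes the later fall look larger in MT or smaller in CGMI-V, so the benefit would be understated.

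**The case against.** The strongest reply is that 6.2.1, the operational section, runs in time order with baseline before randomisation. On this view the consent clause in 9.2.1 is a precondition and not a time point, and the wave text lists what must fit into 8 weeks. If allocation waits for a full wave, and baseline appointments follow consent by a day or two, most baselines would precede allocation. This stands as a possible reading. A reader might infer from 9.2.1 that every baseline will be taken after disclosure; the documents do not support that. They do not exclude it either.

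Three other stronger readings also fail:

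- *MT caregivers who decline the baseline interview would be lost before any data exist.* Every candidate completes the MM-CGI Short Form and PHQ-9 at screening, before consent. These scores cannot be affected by allocation, though they cover only grief and depressive symptoms, and section 9.5 makes no use of them.
- *Early mailing would contaminate the FKAT baseline in the MT arm alone.* MT material is supplied at baseline with no order relative to the interview. CGMI-V materials also include late-stage fact sheets, again with no date relative to baseline. The timing is open in both arms.
- *The shift would manufacture a benefit.* The two reactions described above work against CGMI-V.

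It is also fair that the assumed shift has no source in the documents, and that 8.77 is a one-arm half-width. The ratio to 12.40 is therefore given beside it.

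**Conclusion.** The concern holds as a conflict in the documents with a design consequence. The allocation rule, the schedule and two wave descriptions place randomisation before baseline; a heading order suggests otherwise; no sentence requires baseline first. Some or all baselines may therefore be given by caregivers who know their arm.

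The size is unknown, and it is zero for any caregiver interviewed before disclosure. The 3.6 to 7.2 unit illustration rests wholly on the assumed 0.1 to 0.2 SD shift applied across an arm; if only some baselines follow disclosure, the average shift would be smaller. Full pass-through applies to change and condition-by-time contrasts, and partial pass-through to residualised scores. The point is worth settling because it touches the primary outcome, all secondary outcomes and the mediators, and analysis cannot fully repair it afterwards.

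**What to change.** In 9.2.1, state that each caregiver's baseline CATI interview is completed and recorded in REDCap before that caregiver's assignment is generated and disclosed, and that study materials for either arm are sent only after that interview. Bring the wave text in sections 3, 4.3 and 6.2.1 into the same order, and give randomisation its own column after Baseline in 6.1. Randomising a whole wave in one step is not needed, because the person-level rule is enough.

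Record the dates of interview and disclosure. If any baseline has already followed disclosure, add a sensitivity analysis that uses the screening MM-CGI Short Form and PHQ-9 scores as covariates, noting that they help only for grief and depressive symptoms.

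The cost is wording and a check before assignment. The sample stays at 72 per arm and no assessment is added. Some caregivers learn their arm slightly later.

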9.3 Interim analyses and Stopping Rules

There are no planned interim analyses, as this is a low risk, Stage 1 clinical trial. Interim analyses will only occur if there is a requirement from the Safety Officer in response to specific participant safety issues surrounding the study.

9.4 Outcomes

Multilevel modeling will be used to examine effect sizes associated with both the primary and secondary outcomes. All primary and secondary outcomes will be measured at Baseline, 8 weeks, and 24 weeks.

9.4.1 Primary outcome: Chronic Grief

Caregiver Chronic Grief will be measured with the 50-item Marwit-Meuser Caregiver Grief Inventory (MM-CGI).

9.4.2 Secondary outcomes:

Depressive Symptoms will be measured with the 20-item Center for Epidemiological Studies Depression Scale (CES-D).

Anxiety Symptoms will be measured with the 20-item State-Anxiety subscale of the State-Trait Anxiety Inventory (STAI).

Positive States of Mind will be measured with the 6-item Positive States of Mind Scale (PSOMS).

Conflict with Facility Staff will be measured with the 10-item Conflict with Facility Staff subscale of the Family Perception of Caregiving Role (FPCR).

Satisfaction with Care will be measured with the 51-item Family Perceptions of Care Tool (FPCT).

9.5 Data Analyses

We will track all study participants following CONSORT guidelines and enter all data into a REDCap database. SPSS for Windows (Version 22) and R (Version 3.1.1) will be used for data management and statistical analysis. A two-tailed 0.05 significance level will be used for all statistical tests except where noted below. All analyses will be performed on an intent-to-treat basis. Missing data will be imputed using the R mi package, a multiple imputation computer program based on the work of Rubin.

Histograms will be obtained for these variables, and skew and kurtosis will be assessed to assess statistical normality. From previous research, we expect the error rates to have statistically normal distributions or distributions that can be transformed to normality using logarithmic and square root transformations. We will perform any necessary transformations using Tukey's ladder of transformation before conducting statistical analysis. Because these trials are designed to estimate precise effect sizes rather than probability values, the results of each trial will be the effect size (comparing treatment and control groups) and confidence intervals around this estimate.

Aim 1. Controlling for background variables, establish effect sizes of the CGMI-V condition and Minimal Treatment (MT) control condition on changes in a primary caregiver chronic grief outcome.

Multilevel linear models will be run for the CGMI-V and MT control conditions. Multilevel models are used to estimate autocorrelation across the three time points. We hypothesize that chronic grief will decrease more in the CGMI-V condition relative to the MT control condition. Caregiver sex, age, relationship to the care-receiver, as well as care recipient death or discharge from the facility, will be controlled for as covariates in the analysis. Sex and caregiver/care recipient relationship, as well as care recipient death or discharge from the facility, will be entered into the model as dummy-coded variables. We will examine the interaction effects (δ) to make certain that they are large

enough to justify a more robust clinical trial. While there is some likelihood of obtaining significant findings in this study, the primary purpose of this analysis is to estimate effect sizes.

Aim 2. Controlling for background variables, compare the effect sizes of the CGMI-V condition and MT control condition on changes in secondary caregiver mental health outcomes: depression symptoms and anxiety symptoms and positive states of mind. We hypothesize that one dependent measure (positive states of mind) will increase more and the other two (depression symptoms and anxiety symptoms) will decrease more in the CGMI-V group relative to the MT control condition.

Apart from the dependent measures examined, this analysis will parallel that described in Aim 1. As in Aim 1, the primary goal of this analysis is to estimate effect sizes associated with the CGMI-V.

Aim 3. Controlling for background variables, compare the effect sizes of the CGMI-V condition and MT control condition on secondary facility-related outcomes: caregiver satisfaction with care and conflict with staff in the LTCF. We hypothesize that caregiver satisfaction with care will increase and that conflict with staff in the LTCF will decrease in the CGMI-V condition relative to the MT control condition.

Apart from the dependent measures examined, this analysis will also parallel that described in Aim 1. As in Aim 1, the primary goal of this analysis is to estimate effect sizes associated with the CGMI-V.

Aim 4. Examine the mediating effects of chronic grief exacerbators on chronic grief, mental health, and facility-related outcomes. We hypothesize that improvement in chronic grief exacerbators will mediate the improvements in caregiver chronic grief, mental health, and facility-related outcomes.

The focus of the proposed study is on change in chronic grief, mental health, and facility-related outcomes between measurement points and change in chronic grief exacerbators as a mediating variable. Thus, we propose to use residualized change scores (i.e., the difference between the observed score of a variable and the predicted score based on the baseline measure of that variable) throughout the analyses. These scores have the advantage of evaluating change between measurement points without concerns about regression toward the mean that are associated with standard change scores and have the advantage of reducing the number of variables in the model. In general, the analytic model will include covariates to control for background characteristics of the participants and time since baseline. The mediation effects of changes in chronic grief exacerbators (lack of knowledge, sense of loss, guilt, and role captivity) on three outcome measures (chronic grief, mental health, and facility-related outcomes) will be examined in three separate models. The regression mediation models described in MacKinnon⁷⁶ will be used to estimate these effects. The null hypothesis is that changes in chronic grief exacerbators will not mediate any of the three outcome

measures. As mentioned in the first three aims, the primary goal of this analysis is to estimate the size of these mediation effects, rather than to obtain statistically significant differences.

In accordance with NIH policy we will perform an analysis to estimate effect sizes associated with CGMI-V intervention between gender and racial/ethnic subgroups.

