Intervention: For the CGMI-V intervention condition, study materials (participant manual, technology instructions) will be sent to participants electronically. We will mail hard copies of the manual and technology instructions to those caregivers who prefer to have them printed out. The iPad tablet and the earbuds with microphone will be mailed to participants prior to the first session. As needed, caregivers will receive an individualized over-the-phone orientation (20-30 minutes) in the operation of the equipment from the technology assistant. Each session will start with a brief technology check-up and review of ground rules including maintaining confidentiality.

Each CGMI-V group session will be conducted by one interventionist who has therapeutic group leading experience. For treatment fidelity purposes, the study interventionists will be trained in the delivery of the group intervention and the iPad and online technology. Each group will have not more than six participants. The intervention consists of approximately 60-minute sessions delivered weekly for eight consecutive weeks and will follow the standardized CGMI-V intervention manual (Appendix A).

The purpose of the CGMI-V is to improve ADRD caregivers' (1) knowledge about late-stage ADRD; (2) communication and conflict resolution skills, and (3) skills managing their loss and chronic grief. Sessions 1-2 address caregiver knowledge about late-stage ADRD, and the resources available to dementia families in the LTCF and the community at large.^{3,28} Sessions 3-4 address caregiver skill in communication and conflict resolution and hands-on care in the context of LTCF.^{3,15-17,28-30} Sessions 5-8 address caregiver loss and grief management skills using discussion guides tailored to specific grief management topics.³¹⁻³⁷ The participant manual outlines each session's content and includes questions to facilitate discussion. Additional materials are provided for knowledge and skill topics. These are fact sheets about late-stage ADRD that are published by the Alzheimer's Association, a guide with resources for ADRD family caregivers published by the Family Caregiver Alliance, and a chapter on hospice services (Appendix A).

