Control condition. Caregivers in the control condition will receive Minimal Treatment (MT) consisting of written information about late-stage ADRD (Alzheimer's Association) at baseline. The Project Director will mail caregivers in the MT control condition all written information materials.

4 **SELECTION AND ENROLLMENT OF PARTICIPANTS**

We will recruit a sample of 144 ADRD caregivers who have a family member residing in dementia care or memory care units in long-term care facilities located in the Chicago metropolitan area. We have well-established collaborating relationships with 35 long-term care facilities that will give us access to a diverse pool of approximately 1,000 ADRD family caregivers.

4.1 **Inclusion Criteria**

Participants must meet all inclusion criteria listed below in order to participate in this study.

- 21 years of age or older
- Identified as family member, fictive kin (self-identified family member) or partner of care recipient at any time post permanent placement of care in LTCF
- Care recipient has a documented ADRD diagnosis and resides in any type of unit in a long-term care facility
- Possessing self-reported basic computer literacy and in-home internet access
- Able to speak, read, and write English
- Not currently attending another ADRD caregiver grief management group

- Experiencing high to moderate levels of grief per screening with the Marwit-Meuser Caregiver Grief Inventory-Short Form (scores 25 or above), and/or experiencing high levels of depressive symptoms per screening with PHQ9 (scores 10 or above)
- Caregivers whose care recipients die during the course of the intervention will remain in the study

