9 STATISTICAL CONSIDERATIONS

9.1 General Design Issues

CGMI-V is a Stage I longitudinal randomized clinical trial. ADRD caregivers whose family members are in long-term care facilities (LTCFs) will be recruited, screened for inclusion criteria, and randomly assigned to either CGMI-V or a Minimal Treatment (MT) control condition. Caregivers in the CGMI-V condition will participate in eight weekly professionally led, real-time, live-streaming video online group sessions. Those caregivers in the MT control condition will receive written information materials about late-stage ADRD at baseline. For both conditions, data will be collected at baseline (pre-intervention), 8 weeks (immediately post-intervention) for intervention effects, and 24 weeks post baseline for maintenance effects. The design for this study was chosen to avoid the type of group clustering or contamination that would be engendered by the use of a randomized cluster design. The study hypotheses are outlined below:

Primary Hypothesis

Hypothesis 1: We hypothesize that caregivers in the CGMI-V condition compared to those in the MT control condition, will report decreased chronic grief levels.

Secondary Hypotheses

Hypothesis 2: We hypothesize that caregivers in the CGMI-V condition compared to those in the MT control group will report (2.1) decreased symptoms of depression and anxiety and (2.2) increased positive mental states.

Hypothesis 3.1 and 3.2: We hypothesize that caregivers in the CGMI-V condition compared to those in the MT control condition will report (3.1) increased satisfaction with care provided in the facility and (3.2) decreased conflict with staff.

Mechanism of Intervention Hypothesis

Hypothesis 4: We hypothesize that CGMI-V works by changing the exacerbators of chronic grief: lack of knowledge, sense of loss, guilt, and role captivity.

Primary Outcome Measures

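### The section 9.5 model for Aims 1-3 names no term for the roughly 12 CGMI-V therapy groups, so its confidence interval is too narrow unless the group ICC is near zero

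*Combined protocol and SAP*

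**What the plan says.** Section 3 (Intervention) describes group delivery: "Each group will have not more than six participants", and "Each CGMI-V group session will be conducted by one interventionist". The control condition in the same section has no groups: "The Project Director will mail caregivers in the MT control condition all written information materials". Section 9.2.1 sets the enrolment pattern: "Randomization will be stratified in six Waves of 24 participants each", with 12 caregivers per condition in each wave and CGMI-V run as six per group.

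For Aim 1, section 9.5 gives the reason for a multilevel model: "Multilevel models are used to estimate autocorrelation across the three time points". The covariates are caregiver sex, age, relationship to the care recipient, and the care recipient's death or discharge. Aims 2 and 3 take over this analysis with other outcomes. On missing data the section says "Missing data will be imputed using the R mi package", without mention of group, and the Aim 4 mediation models do not mention it either. Section 9.5 also states what the trial will report: "the results of each trial will be the effect size (comparing treatment and control groups) and confidence intervals around this estimate".

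Clustering is mentioned once, in section 9.1, where the design is said to have been chosen to "avoid the type of group clustering or contamination that would be engendered by the use of a randomized cluster design".

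**The concern.** Individual randomisation makes caregivers independent at baseline. It does not keep them independent after eight weekly sessions with the same few people and the same leader. The design is partially nested: about 12 clusters in one arm and unclustered individuals in the other. The section 9.1 sentence is right about clustering from a cluster-randomised design, but does not cover clustering created by the way the treatment is given.

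If the model treats the CGMI-V caregivers as independent, the variance of that arm's mean is understated whenever group members resemble each other at follow-up. The point estimate need not be biased; the damage is to the interval. That matters here because the plan puts precision ahead of testing, reports the effect size with its interval as the result, and uses the effect to judge whether a larger trial is justified.

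**Working it through.** **Inputs from the documents.** SD 35.78 and 64 analysed per arm (section 9.2); 72 enrolled per arm; 12 CGMI-V caregivers per wave in groups of six, six waves (section 9.2.1). Number of groups: (12/6) × 6 = 12. Analysed group size: 64/12 = 5.33; full group size: 6.

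**The plan's own figure.** 35.78/√64 = 4.47, and 1.96 × 4.47 = 8.77, as section 9.2 states. This is the interval for one arm's mean. The between-arm difference is what Aim 1 estimates, and its half-width before any clustering is 1.96 × 35.78 × √(2/64) = 12.40. That is the reference value below.

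**Assumed.** The documents give no ICC; .01 to .10 is an illustrative range. ICC here means the group share of follow-up score variance in the CGMI-V arm.

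**Single follow-up score.** The design effect in the CGMI-V arm is 1 + (m − 1) × ICC, and 1 in the control arm. With equal arms the variance of the difference is multiplied by k = 1 + (m − 1) × ICC/2. The correct half-width is 12.40 × √k, and actual coverage of the interval that ignores groups is 2Φ(1.96/√k) − 1.

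| m | ICC | k | Correct half-width | Wider by | Actual coverage |
|---|---|---|---|---|---|
| 5.33 | .01 | 1.022 | 12.53 | 1.1% | 94.8% |
| 5.33 | .05 | 1.108 | 13.05 | 5.3% | 93.7% |
| 5.33 | .10 | 1.217 | 13.67 | 10.3% | 92.4% |
| 6 | .01 | 1.025 | 12.55 | 1.2% | 94.7% |
| 6 | .05 | 1.125 | 13.15 | 6.1% | 93.5% |
| 6 | .10 | 1.250 | 13.86 | 11.8% | 92.0% |

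The m = 5.33 rows match 64 analysed per arm. A simulation with full groups (12 groups of 6 against 72 individuals, 40,000 runs) gave 94.8%, 93.3% and 92.0%.

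**Change from baseline.** Groups do not exist at baseline, so taking out baseline shrinks the individual variance but not the group variance. With total variance 1 and within-person correlation r, the group share becomes ICC/[2(1 − r)] for simple change and ICC/(1 − r²) for a baseline-adjusted score. Two values of r are assumed: .5, and .71, the low end of the test-retest range in section 9.1, which is for the subscales and has no stated retest interval.

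Worked case, r = .71, ICC .10, m = 5.33, simple change: share = .10/.58 = .172; k = 1 + 4.33 × .172/2 = 1.374; √k = 1.172; coverage about 90.5%.

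Simulated coverage, 64 per arm in 12 groups, group ignored, 40,000 runs (simple change / baseline-adjusted):

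| r | ICC 0 | ICC .01 | ICC .05 | ICC .10 |
|---|---|---|---|---|
| .5 | 94.9 / 94.9% | 94.7 / 94.5% | 93.7 / 93.4% | 92.3 / 91.5% |
| .71 | 95.1 / 94.9% | 94.6 / 94.4% | 92.6 / 92.1% | 90.5 / 89.7% |

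**Wave.** Arms are balanced 12:12 within wave, so wave differences cancel in the contrast. With an assumed 10% wave share, ICC 0 and 72 per arm, omitting wave gave 95.9% coverage for a single score and 95.1% for change. Omission is therefore harmless or slightly conservative.

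**The case against.** - **A group level is not excluded.** The plan commits to multilevel models, and stating one purpose does not rule out another level. That is fair as a reading. But no group level is specified, so an analyst following the text would fit none.
- **The size rests on assumption.** This stands. At ICC .01 the effect is negligible, and the figures near 90% need both ICC .10 and a correlation of .71 borrowed from the subscales. One ICC is also used for both follow-ups, although the groups stop meeting at 8 weeks and the last assessment is at 24.
- **The contrast is less open than two versions suggest.** Aim 1 speaks of greater decrease and of interaction effects, which points to condition-by-time change. The simple-change figures are then the nearer ones, and the baseline-adjusted figures are the worse of each pair.
- **The correction has a price.** A group variance held at zero or above costs more than a group-means analysis when there is no clustering: an approximate check with wave fitted gave a half-width of 0.272 against 0.251 SD (about 8%), with 96.1% coverage; without wave it is about 0.264 SD (about 5%). This is correct and belongs in the decision.
- **A Stage I trial could make do with a sensitivity analysis and a stated limitation.** The early stage does limit the severity. Yet the interval is what this trial sets out to deliver, so its main version should have the right width.

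**Conclusion.** The concern holds. About 12 therapy groups in one arm follow directly from the documents, and the specified analysis does not account for them. For any non-trivial positive group ICC the reported interval for Aims 1-3 claims more precision than the trial has.

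The size is unknown because no ICC is given. Over the assumed range it runs from negligible at .01 (about 1% on the half-width) to about 10% at .10 for a single score, with coverage near 92%. For simple change, coverage is 92.3% at ICC .10 with correlation .5 and 90.5% with .71. The effect estimate itself need not be biased. This should be fixed, but it does not undermine the design. Confidence is high that the omission is real; the amount of harm depends on an ICC that cannot be learned from the documents.

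**What to change.** **Changes.**

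1. Section 9.5, Aims 1-3: add a therapy-group random effect for the CGMI-V arm only, at post-baseline times, with control caregivers as singletons and Kenward-Roger or Satterthwaite degrees of freedom.
2. Carry the group structure into the multiple imputation and the Aim 4 models.
3. Report the group ICC with its interval and say that it is imprecise.
4. Section 9.2: show the precision of the two-arm difference over a stated, assumed ICC range, for example .01 to .10.
5. Section 9.1: keep the sentence and add that individual randomisation does not remove clustering created by group delivery.
6. Separately, add wave as a fixed factor so that the analysis matches the stratified randomisation. This is a matter of consistency and does not cure the narrow interval; it also lowers the group degrees of freedom from 11 to 6.

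**Cost.** No new data, since group and wave are known for everyone. The work is model text, a precision paragraph and possibly an imputation routine that handles clusters.

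The interval widens. Simulated example: group-level Satterthwaite analysis of change, 72 per arm, correlation .71 assumed, wave fitted.

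| ICC | Half-width, group ignored (SD) | Half-width, adjusted (SD) | Coverage, ignored → adjusted |
|---|---|---|---|
| 0 | 0.250 | 0.261 | – |
| .05 | 0.250 | 0.292 | 92.5% → 94.9% |
| .10 | 0.250 | 0.320 | 90.0% → 94.9% |

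The price at ICC 0 is about 4% here (0.261/0.250), and about 5% to 8% if the group variance is constrained to be non-negative.

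The group variance will be poorly estimated. For a single score with full groups, the chance of a zero or negative moment estimate is P[F(df, 60) ≤ (1 − ICC)/(1 + 5 × ICC)]: 32% at ICC .05 and 18% at .10 with 11 df, or 40% and 27% with 6 df. An observed ICC of .05 would have a 95% interval of about −.07 to .33 (11 df) or −.09 to .48 (6 df). The plan should therefore state that the group term stays in the model whatever its estimate.
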